4.2.1. Choice of Contraception/Barrier Requirements

There is no suspicion of human teratogenicity based on the intended pharmacology of the compound. Human reproductive safety data are limited for sisunatovir, therefore the use of a highly effective method of contraception is required for all female participants (see [Appendix 4](#)).

4.2.2. Collection of Retained Research Samples

Retained Research Samples will be collected and stored for further analyses which may, for example, provide greater understanding of the study intervention.

4.2.3. Collection of Retained Research Samples

Retained Research Samples will be collected and stored for further analyses which may, for example, provide greater understanding of the study intervention.

4.3. Justification for Dose

To investigate the effect of sisunatovir on clinical activity following RSV infection, a viral challenge clinical study in healthy participants was conducted where doses of 200 mg or 350 mg Q12 x 5 days were administered following inoculation of an RSV infection. In this study, at both doses evaluated, sisunatovir robustly decreased viral load and alleviated RSV symptoms relative to placebo. While statistically significant differences were not observed between the two dose levels, the 350 mg dose was numerically superior to the 200 mg dose.

While these data demonstrate pharmacological activity, effects in the viral challenge study have not translated to robust effects in clinical trials evaluating patient populations (ie, in treatment of RSV). One possible reason for this is that in the treatment of RSV drug intervention occurs several days after infection whereas the proximity of start of treatment to infection in the viral challenge study is much sooner. For this reason, it is desired to dose sisunatovir Phase 2/3 efficacy studies at doses that maximize coverage over EC90 at a safe

and well tolerated dose. Additionally, dosing at higher multiples over EC90 may confer protection against resistance.

Sisunatovir was generally well tolerated in the viral challenge study as well as other Phase 1 studies conducted to date. However, an increased incidence of GI AEs were observed at the 350 mg dose relative to the 200 mg dose. Higher rates of GI AEs were also observed at higher doses within the Phase 1 program. In these studies, sisunatovir was dosed in a fasted state. Although improved GI tolerability has been observed for some anti-infective agents when dosed with food, it is not clear if GI tolerability of sisunatovir will improve with food.

The primary purpose of Cohort 1 of this study is to evaluate the safety and tolerability of the 400 mg Q12 hours x 4 days plus one dose dosing regimen and if any potential GI AEs can be mitigated with food. Therefore, within the first 2 periods of Cohort 1, each participant will receive 400 mg Q12 hours x 4 days plus 1 dose of sisunatovir with food (compared to placebo or 200 mg Q12hours). In Period 3 of Cohort 1, participants will receive 400 mg Q12 hours x 4 days plus 1 dose fasted to directly compare PK, safety and tolerability in the same participants dosed fed at the same dose level. Note doses in Periods 2 and 3 may be adjusted based on PK and safety findings from the previous dosing periods (see [Section 4.1](#)).

The effect of food on the pharmacokinetics of sisunatovir has been variable in Phase 1 studies. However, the effect of food on the pharmacokinetics of sisunatovir using the formulation to be used in this study (dry powder blend in capsules) showed minimal food effect.

As the exposure of sisunatovir increases in a greater than dose proportional manner, the steady state exposure at the planned dose in Cohort 1 (400 mg Q12 hours) is expected to be ~40% greater than the exposure at the highest dose studied to date (350 mg Q12 hours). At this dose, the anticipated safety margin over rat (most sensitive species) NOAEL AUC and C_{max} in the 28-day toxicology study are 1.2-fold.

Cohort 2 in this study is optional and will only be conducted at the discretion of the sponsor after reviewing data from Cohort 1. The dose assessed in Cohort 2 will not exceed 400 mg Q12 hours x 5 days or a dose that is projected to exceed the rat NOAEL based on Cohort 1 PK data. This cohort may be used to assess a lower dose (e.g., 300 mg) or may be used to collect additional data at the same dose that has been tested in Cohort 1 and is viewed as safe. These data may then be used to define the dose and dosing instructions in Phase 2/3.

The dose for the palatability cohort (50 mg in a 7 mL dosing solution) was selected to be close to the anticipated drug concentration in pediatric studies.

4.4. End of Study Definition

The end of the study is defined as the date of the last visit of the last participant in the study.

A participant is considered to have completed the study if they have completed all periods of the study, including the last visit.

5. STUDY POPULATION

This study can fulfill its objectives only if appropriate participants are enrolled, including participants across diverse and representative racial and ethnic backgrounds. Use of a prescreening tool is utilized for study recruitment purposes, it will include collection of information that reflects the enrollment of a diverse participant population including, where permitted under local regulations, age, sex, and race, and ethnicity. The following eligibility criteria are designed to select participants for whom participation in the study is considered appropriate. All relevant medical and nonmedical conditions should be taken into consideration when deciding whether a particular participant is suitable for this protocol.

Prospective approval of protocol deviations to recruitment and enrollment criteria, also known as protocol waivers or exemptions, is not permitted.

5.1. Inclusion Criteria

Participants are eligible to be included in the study only if all of the following criteria apply:

Age and Sex:

1. Participants aged 18 to 65 years of age, inclusive, at the time of signing of the ICD.
 - All fertile participants must agree to use a highly effective method of contraception.
 - Refer to [Appendix 4](#) for reproductive criteria for male ([Section 10.4.1](#)) and female ([Section 10.4.2](#)) participants.
2. Male and female participants who are overtly healthy as determined by medical evaluation including medical history, physical examination, including blood pressure, pulse rate, standard 12-lead ECG, and laboratory tests.

Other Inclusion Criteria:

3. BMI of 17.5 to 35 kg/m²; and a total body weight >50 kg (110 lb).
4. Capable of giving signed informed consent as described in [Appendix 1: Regulatory, Ethical, and Study Oversight Considerations](#) which includes compliance with requirements and restrictions listed in the ICD and in this protocol.

5.2. Exclusion Criteria

Participants are excluded from the study if any of the following criteria apply:

Medical Conditions:

1. Evidence or history of clinically significant hematological, renal, endocrine, pulmonary, gastrointestinal, cardiovascular, hepatic, psychiatric, neurological, or

allergic disease (including drug allergies, but excluding untreated, asymptomatic, seasonal allergies at the time of dosing).

- Any condition possibly affecting drug absorption (eg, gastrectomy, cholecystectomy).
- History of HIV infection, hepatitis B, or hepatitis C; positive testing for HIV, HBsAg, or HCVAb. Hepatitis B vaccination is allowed.
- Positive test result for SARS-CoV-2 infection on Day -1.

2. Other medical or psychiatric condition including recent (within the past year) or active suicidal ideation/behavior or laboratory abnormality or other conditions or situations related to COVID-19 pandemic that may increase the risk of study participation or, in the investigator's judgment, make the participant inappropriate for the study.

Prior/Concomitant Therapy:

3. Use of prescription or nonprescription drugs and dietary and herbal supplements within 7 days or 5 half-lives (whichever is longer) prior to the first dose of study intervention with the exception of moderate/strong CYP3A inducers or time-dependent inhibitors which are prohibited within 14 days plus 5 half-lives prior to the first dose of study intervention. (Refer to [Section 6.9](#) for additional details).
4. Current use of any prohibited concomitant medication(s) or participant unwilling/unable to use a permitted concomitant medication(s).
5. Female participants taking hormonal contraceptives or hormone replacement therapy within 28 days of the first dose of study treatment.
 - Injectable hormone therapy (eg, DepoProvera[®]) must be discontinued at least 6 months prior to the first dose of study treatment.

Prior/Concurrent Clinical Study Experience:

6. Previous administration with an investigational product (drug or vaccine) within 30 days (or as determined by the local requirement) or 5 half-lives preceding the first dose of study intervention used in this study (whichever is longer).

Diagnostic Assessments:

7. A positive urine drug test, confirmed by a repeat test, if deemed necessary.
8. Screening supine BP ≥ 140 mm Hg (systolic) or ≥ 90 mm Hg (diastolic), following at least 5 minutes of supine rest. If BP is ≥ 140 mm Hg (systolic) or ≥ 90 mm Hg

(diastolic), the BP should be repeated 2 more times and the average of the 3 BP values should be used to determine the participant's eligibility.

9. Standard 12-lead ECG that demonstrates clinically relevant abnormalities that may affect participant safety or interpretation of study results (eg, QTcF >450 ms, complete LBBB, signs of an acute or indeterminate- age myocardial infarction, ST-T interval changes suggestive of myocardial ischemia, second- or third- degree AV block, or serious bradyarrhythmias or tachyarrhythmias). If the uncorrected QT interval is >450 ms, this interval should be rate-corrected using the Fridericia method only and the resulting QTcF should be used for decision making and reporting. If QTcF exceeds 450 ms, or QRS exceeds 120 ms, the ECG should be repeated twice and the average of the 3 QTcF or QRS values used to determine the participant's eligibility. Computer-interpreted ECGs should be overread by a physician experienced in reading ECGs before excluding a participant.
10. Participants with **ANY** of the following abnormalities in clinical laboratory tests at screening, as assessed by the study-specific laboratory and confirmed by a single repeat test, if deemed necessary:
 - eGFR <60 mL/min/1.73m² based on CKD-EPI equation;
 - AST **or** ALT level $\geq 1.5 \times$ ULN;
 - Gamma-GT $>$ ULN;
 - Alkaline phosphatase $>$ ULN;
 - Total bilirubin level $\geq 1.5 \times$ ULN; participants with a history of Gilbert's syndrome may have direct bilirubin measured and would be eligible for this study provided the direct bilirubin level is \leq ULN.

Other Exclusion Criteria:

11. History of alcohol abuse or binge drinking and/or any other illicit drug use or dependence within 6 months of Screening. Binge drinking is defined as a pattern of 5 (male) and 4 (female) or more alcoholic drinks in about 2 hours. As a general rule, alcohol intake should not exceed 14 units per week (1 unit = 8 ounces (240 mL) beer, 1 ounce (30 mL) of 40% spirit, or 3 ounces (90 mL) of wine).
12. Blood donation (excluding plasma donations) of approximately 1 pint (500 mL) or more within 60 days prior to dosing.
13. History of sensitivity to sisunatovir or any of the formulation components.
14. Use of tobacco or nicotine-containing products in excess of the equivalent of 5 cigarettes/day or 2 chews of tobacco/day.

15. Unwilling or unable to comply with the criteria in the Lifestyle Considerations section of this protocol.
16. Investigator site staff directly involved in the conduct of the study and their family members, site staff otherwise supervised by the investigator, and sponsor and sponsor delegate employees directly involved in the conduct of the study and their family members.

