6.9. Prior and Concomitant Therapy

Use of prescription or nonprescription drugs and dietary and herbal supplements are prohibited within 7 days or 5 half-lives (whichever is longer) prior to the first dose of study intervention. Limited use of nonprescription medications that are not believed to affect participant safety or the overall results of the study may be permitted on a case-by-case basis

following approval by the sponsor. Acetaminophen/paracetamol may be used at doses of ≤ 1 g/day.

Females using hormonal contraceptives or taking hormone replacement therapy may be eligible to participate in this study if they are willing to discontinue therapy at least 28 days prior to the first dose of study treatment and remain off hormonal therapy for the duration of the study. DepoProvera® must be discontinued at least 6 months prior to the first dose of study treatment.

All concomitant treatments taken during the study must be recorded with indication, daily dose, and start and stop dates of administration. All participants will be questioned about concomitant treatment at each clinic visit.

Treatments taken within 28 days before the first dose of study intervention will be documented as a prior treatment. Treatments taken after the first dose of study intervention will be documented as concomitant treatments.

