10.4. Appendix 4: Contraceptive and Barrier Guidance

10.4.1. Male Participant Reproductive Inclusion Criteria

Male participants are eligible to participate if they agree to the following requirements during the intervention period and for at least 28 days after the last dose of study intervention, which corresponds to the time needed to eliminate reproductive safety risk of the study intervention(s):

- Refrain from donating sperm.

PLUS either:

- Be abstinent from heterosexual intercourse as their preferred and usual lifestyle (abstinent on a longterm and persistent basis) and agree to remain abstinent.

OR

- Must agree to use contraception/barrier as detailed below:
 - Agree to use a male condom[, and should also be advised of the benefit for a female partner to use a highly effective method of contraception, as a condom may break or leak,] when having sexual intercourse with a WOCBP who is not currently pregnant.
 - In addition to male condom use, a highly effective method of contraception may be considered in WOCBP partners of male participants (refer to the list of highly effective methods below in [Section 10.4.4](#)).

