10.4.3. Woman of Childbearing Potential

A woman is considered fertile following menarche and until becoming postmenopausal unless permanently sterile (see below).

If fertility is unclear (eg, amenorrhea in adolescents or athletes) and a menstrual cycle cannot be confirmed before the first dose of study intervention, additional evaluation should be considered.

Women in the following categories are not considered WOCBP:

1. Premenopausal female with 1 of the following:

- Documented hysterectomy;
- Documented bilateral salpingectomy;
- Documented bilateral oophorectomy.

For individuals with permanent infertility due to a medical cause other than the above (eg, mullerian agenesis, androgen insensitivity), investigator discretion should be applied to determining study entry.

Note: Documentation for any of the above categories can come from the site personnel's review of the participant's medical records, medical examination, or medical history interview. The method of documentation should be recorded in the participant's medical record for the study.

2. Postmenopausal female.

- A postmenopausal state is defined as no menses for 12 months without an alternative medical cause. In addition:
 - A high FSH level in the postmenopausal range must be used to confirm a postmenopausal state in women under 60 years old and not using hormonal contraception or HRT.
 - A female on HRT and whose menopausal status is in doubt will be required to use one of the highly effective nonestrogen hormonal contraception methods if she wishes to continue her HRT during the study. Otherwise, she must

discontinue HRT to allow confirmation of postmenopausal status before study enrollment.

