10.4.4. Contraception Methods

Contraceptive use by men or women should be consistent with local availability/regulations regarding the use of contraceptive methods for those participating in clinical trials.

The following contraceptive methods are appropriate for this study:

Highly Effective Methods That Have Low User Dependency

1. Implantable progestogen-only hormone contraception associated with inhibition of ovulation.
2. Intrauterine device.
3. Intrauterine hormone-releasing system.
4. Bilateral tubal occlusion.
5. Vasectomized partner:
 - Vasectomized partner is a highly effective contraceptive method provided that the partner is the sole sexual partner of the WOCBP and the absence of sperm has been confirmed. If not, an additional highly effective method of contraception should be used. The spermatogenesis cycle is approximately 90 days.

Highly Effective Methods That Are User Dependent

6. Progestogen only hormone contraception associated with inhibition of ovulation:
 - Oral + barrier*.
 - Injectable + barrier*.

Sexual Abstinence

7. Sexual abstinence is considered a highly effective method only if defined as refraining from heterosexual intercourse during the entire period of risk associated with the study intervention. The reliability of sexual abstinence needs to be evaluated in relation to the duration of the study and the preferred and usual lifestyle of the participant.

* Acceptable barrier methods to be used concomitantly with option 6 for the study include any of the following:

- Male or female condom, with or without spermicide;
- Cervical cap, diaphragm or sponge with spermicide;
- A combination of male condom with either cervical cap, diaphragm or sponge with spermicide (double-barrier methods).

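### Exclusion 5 and Section 6.9 bar hormonal contraception and HRT for female participants, while Appendix 4, as part of Inclusion 1, permits hormonal methods and, in one case, continued HRT; the passages must be reconciled

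*Protocol*

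**What the plan says.** **The restriction.** Protocol Section 5.2, criterion 5, excludes "Female participants taking hormonal contraceptives or hormone replacement therapy within 28 days of the first dose of study treatment". Its sub-bullet says that injectable hormone therapy "must be discontinued at least 6 months prior to the first dose of study treatment". Section 6.9 carries the rule into the study. It admits women who use hormonal contraception or HRT on one condition, which runs until their participation ends: that they be "willing to discontinue therapy at least 28 days prior to the first dose of study treatment and remain off hormonal therapy for the duration".

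**The permission.** Section 10.4.2 states that its female reproductive criteria belong to Inclusion Criterion 1, and it points to Section 10.4.4 as the complete list of permitted methods. Section 10.4.4 opens with "The following contraceptive methods are appropriate for this study". Its first item is "Implantable progestogen-only hormone contraception associated with inhibition of ovulation". Item 3 is a hormone-releasing intrauterine system, and item 6 is oral or injectable progestogen with a barrier. Under Section 10.4.3, a woman on HRT whose menopausal status is in doubt is to "use one of the highly effective nonestrogen hormonal contraception methods if she wishes to continue her HRT during the study"; otherwise she must stop HRT.

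**The male requirement.** Inclusion 1 in Section 5.1 says: "All fertile participants must agree to use a highly effective method of contraception". Section 10.4.1, to which that criterion refers for men, accepts a male condom (or abstinence) and says that "a highly effective method of contraception may be considered in WOCBP partners of male participants".

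**The concern.** Eligibility criteria should give one answer for one person. Here a woman with a progestogen implant meets the contraceptive part of Inclusion 1, by a method that the protocol itself lists, and is excluded by criterion 5 for using it. The on-study rule in Section 6.9 and the list in Section 10.4.4 conflict in the same way after enrolment.

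Two things are at stake. A site that works from Appendix 4 may enrol or keep a woman on a drug that the plan meant to keep out; criterion 5 stands under the heading for prior and concomitant therapy. A site that works from criterion 5 and Section 6.9 may ask a woman to stop a method that Appendix 4 accepts. Section 4.2.1 meanwhile requires highly effective contraception of all female participants because human reproductive safety data are limited. Section 5 forbids waivers of enrolment criteria, so a wrong enrolment cannot be approved in advance.

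**Working it through.** There is no figure to reproduce and the point needs no calculation beyond a count. The check sets the passages side by side.

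**1. The listed methods against criterion 5 and Section 6.9**

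| Item in Section 10.4.4 | Hormonal? | Compatible with 5.2(5) and 6.9? |
|---|---|---|
| 1 Progestogen implant | Yes | No |
| 2 Intrauterine device | No | Yes |
| 3 Hormone-releasing intrauterine system | Yes | No |
| 4 Bilateral tubal occlusion | No | Yes |
| 5 Vasectomized partner | No | Yes |
| 6 Oral or injectable progestogen plus barrier | Yes | No (for the injectable, a 6-month limit applies) |
| 7 Abstinence | No | Yes |

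Conflicting: items 1, 3 and 6, so 3 of 7. Compatible: items 2, 4, 5 and 7, so 7 − 3 = 4. Item 3 is counted because criterion 5 speaks of hormonal contraceptives without exempting any route. If the sponsor meant to exempt the intrauterine system, the count falls to 3 − 1 = 2 of 7, and the conflict remains.

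**2. HRT.** The allowance in Section 10.4.3 has two conditions: doubtful menopausal status, and use of a nonestrogen hormonal contraceptive. A woman who meets both is on two therapies, and criterion 5 and Section 6.9 bar each of them.

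**3. Which text governs?** Section 5.1 requires every inclusion criterion to be met, and Section 5.2 excludes on any single criterion. Read strictly, criterion 5 therefore decides and the woman is not eligible. No text says so in relation to Appendix 4, and Appendix 4 mentions neither criterion 5 nor Section 6.9.

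**4. How following the text goes wrong.**
- Section 5.3.1 tells the investigator to confirm the method from the permitted list in Appendix 4. It cites Section 10.4.3, but the list is in Section 10.4.4.
- Section 8.3.6 says that suitable contraception must be started after the negative pregnancy test at screening. The Schedule of Activities places screening between Day -28 and Day -2.
- A woman who then starts item 1, 3 or 6 is using a hormonal method in the 28 days before the first dose (criterion 5). If she continues, she is also on it during the study (Section 6.9).

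Each step is an instruction in the protocol, and together they produce an excluded participant.

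**5. Who the list serves.** Section 10.4.2 applies Section 10.4.4 to female participants. Section 10.4.1 applies the same list to partners of male participants. Criterion 5 covers female participants only, so items 1, 3 and 6 conflict in the first use and not in the second.

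**6. Men.** Inclusion 1 asks a highly effective method of all fertile participants. Section 10.4.1 requires a condom or abstinence and makes a highly effective partner method optional. A man using a condom alone satisfies Section 10.4.1 and does not satisfy the bullet in Inclusion 1.

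**The case against.** The strongest reply is that nothing is undecided: meeting Appendix 4 is necessary but not sufficient, Section 8.1 requires all eligibility criteria to be confirmed, and a numbered exclusion repeated in Section 6.9 is hard to miss. Concomitant treatments are recorded at each clinic visit, and Appendix 9 requires the sponsor to be consulted on any concomitant medication, so hormonal use would probably come to light. On the strict logic this is right, and it limits the likely number of wrong enrolments. It does not excuse text that calls a method permitted and appropriate for the study while another section excludes its users.

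It can also be said that the hormonal items are there for partners of male participants. That explains why they might appear, but Section 10.4.2 applies the undivided list to female participants.

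On men, the bullet beneath the Inclusion 1 wording refers to Section 10.4.1, and Section 4.2.1 states the highly effective requirement for female participants only. The discrepancy is therefore minor and signposted, though it is still there.

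Some stronger readings are tempting, and the documents do not support them:
- *Contraceptive protection and the drug restriction are incompatible.* They are not; four of the seven methods satisfy both.
- *A 28-day stop cannot follow consent within a 28-day screening window.* The two rules do not contradict each other. Section 5.4 allows rescreening, and other look-back periods (30 days in criterion 6, 60 days in criterion 12) also reach back before screening.
- *HRT may generally continue under Appendix 4.* The allowance covers only the conditional case in Section 10.4.3.
- *Hormonal use would distort the PK results.* The documents give no figure for such an effect.

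**Conclusion.** The inconsistency is real and lies in current operative text. For female participants, 3 of the 7 listed methods (2 of 7 if the intrauterine system was meant to be exempt) and the conditional HRT allowance conflict with criterion 5 and Section 6.9. The strict reading excludes these women, but the contraception check and the instruction to start contraception after screening can lead a site to the opposite result. The mismatch between Inclusion 1 and Section 10.4.1 for men is a separate, smaller defect.

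The conclusion assumes that hormonal contraceptives in criterion 5 has its ordinary meaning and that no other document sets an order of precedence. It concerns eligibility and participant protection. The statistical analysis is not affected as planned, and the documents do not allow the number of affected participants or any effect on exposure to be estimated. It should be corrected because it bears on who may be dosed and the correction is cheap.

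**What to change.** The sponsor should:

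1. Reconcile Section 5.2 (criterion 5) and Section 6.9 with Sections 10.4.2, 10.4.3 and 10.4.4, so that one rule on hormonal contraception and HRT applies to female participants throughout.
2. State in Section 10.4.4 which methods apply to female participants and which to partners of male participants. Simply striking the hormonal items would also remove them for partners, for whom they do not conflict with anything.
3. Reconcile the bullet in Inclusion 1, which the synopsis repeats, with Section 10.4.1.
4. Correct the cross-reference in Section 5.3.1 from Section 10.4.3 to Section 10.4.4.

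Which rule is right, for women or for men, is a clinical decision for the sponsor, and none is proposed here. The cost is a wording amendment to the synopsis, Sections 5.1, 5.2, 5.3.1 and 6.9 and Appendix 4 as needed, with the ethics approval that Section 10.1.1 requires. Depending on the rule chosen, some women may become ineligible or need to change method before dosing. Sample size, endpoints and the SAP are unchanged.
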